9.2. Exclusion Criteria

1. Radiotherapy treatment within 4 weeks of starting veledimex
2. Prior treatment with bevacizumab
3. Subjects receiving systemic corticosteroids for treatment of disease-related symptoms during the 4 weeks prior to Day -7
4. Subjects with clinically significant increased intracranial pressure (e.g., impending herniation or requirement for immediate palliative treatment) or uncontrolled seizures
5. Uncontrolled infection with human immunodeficiency virus, hepatitis B or hepatitis C infection; or diagnosis of immunodeficiency.

NOTE:

- Subjects with known HIV infection who have controlled infection (undetectable viral load (HIV RNA PCR) and CD4 count above 350 either spontaneously or on a stable antiviral regimen) are permitted. For subjects with controlled HIV infection, monitoring will be performed per local standards.
- Subjects with hepatitis B (HBsAg+) who have controlled infection (serum hepatitis B virus DNA PCR that is below the limit of detection AND receiving anti-viral therapy for hepatitis B) are permitted. Subjects with controlled infections must undergo periodic monitoring of HBV DNA. Subjects must remain on anti-viral therapy for at least 6 months beyond the last dose of investigational study drug.

- Subjects who are hepatitis C virus antibody positive (HCV Ab+) who have controlled infection (undetectable HCV RNA by PCR either spontaneously or in response to a successful prior course of anti-HCV therapy) are permitted.

6. Use of systemic antibacterial, antifungal, or antiviral medications for the treatment of acute clinically significant infection within 2 weeks of first veledimex dose. Concomitant therapy for chronic infections is not allowed. Subjects must be afebrile prior to Ad-RTS-hIL-12 injection; only prophylactic antibiotic use is allowed perioperatively.
7. Use of enzyme-inducing antiepileptic drugs (EIAED) within 7 days prior to the first dose of study drug. Note: Levetiracetam (Keppra®) is not an EIAED and is allowed.
8. Other concurrent clinically active malignant disease, requiring treatment, except for non-melanoma cancers of the skin or carcinoma in situ of the cervix or non-metastatic prostate cancer
9. Nursing or pregnant females
10. Prior exposure to veledimex
11. Use of an investigational product within prior 30 days.
12. Prior exposure to inhibitors of immuno-checkpoint pathways (e.g., anti-PD-1, anti-PD-L1, anti-PD-L2, anti-CD137, or anti-CTLA-4 antibody) or other agents specifically targeting T cells.
13. Use of medications that induce, inhibit, or are substrates of CYP450 3A4 prior to veledimex dosing without consultation with the Medical Monitor
14. Presence of any contraindication for a neurosurgical procedure
15. Use of heparin or other anti-coagulation therapy, or acetylsalicylic acid (ASA), or anti-platelet drug within Day -7 to Day 21 should not be used unless necessary to treat a life-threatening illness. Prophylactic subcutaneous heparin per institutional protocol for prevention of DVT may be allowed based on discussion with the Medical Monitor. Concomitant medications should continue to be reviewed in consultation with the Medical Monitor.
16. Unstable or clinically significant medical condition that would, in the opinion of the Investigator or Medical Monitor, jeopardize the safety of a subject and/or their compliance with the protocol. Examples include, but are not limited to, history of myocarditis or congestive heart failure (as defined by New York Heart Association Functional Class III or IV), unstable angina, serious uncontrolled cardiac arrhythmia, myocardial infarction within 6 months of screening, active interstitial lung disease (ILD)/pneumonitis or a history of ILD/pneumonitis requiring treatment with systemic steroids uncontrolled asthma, or colitis.

9.3. Subject Enrollment

Approximately 36 subjects may be enrolled.

9.4. Withdrawal of Subjects from Study Treatment and/or Study

The sponsor may terminate this study at any time. The investigator and/or the subject have the right to terminate the subject's participation in the study at any time. Efforts should be made to ask subjects who discontinue study drug to be available to complete the Follow-up assessments.

A subject may withdraw or be withdrawn from the study treatment prematurely for any of the following reasons:

- Principal Investigator (PI) determines further participation is not in the subject's best interest (e.g., subject experiences rapid clinical deterioration in the absence of confirmed disease progression)
- Subject has confirmed disease progression
- A subject must be withdrawn in the event of any of the following:
 - Subject withdraws informed consent.
 - Any treatment-related AEs that meet withdrawal criteria
 - Substantial noncompliance with study requirements
 - Subjects with a confirmed positive pregnancy test
 - Any intercurrent illness that would, in the judgement of the investigator or sponsor's medical monitor, affect assessments of clinical status to a significant degree and require discontinuation of protocol therapy
 - Subjects who did not receive any study drugs
- *NOTE: Any subject who wishes to withdraw from the study treatment may do so at any time but will be asked to be available for the safety, tumor response, and survival follow-up assessments.*

Every effort should be made to follow subjects who withdraw from study treatment for ongoing treatment-related AEs. Subjects who withdraw during the treatment period should continue to have study assessments as clinically indicated.

9.5. Replacement of Subjects

Subjects who withdraw from the study or do not receive each study drug may be replaced. All dosed subjects will be included in the overall safety assessment.

9.6. Premature Termination of Study or Study Site

The sponsor has the right to close the study at any time, although this should occur only after mutual consultation between the sponsor and the investigators. The Institutional Review Board (IRB) or Independent Ethics Committee (IEC) must be informed of such action. Should the study or center be closed prematurely, all study materials (completed, partially completed, and blank electronic case report forms (eCRF), study medication, etc.) must be stored or disposed of according to the sponsor's instructions. Events that may trigger premature termination of the study or closure of a center include but are not limited to the following: new toxicity findings; decision to re-challenge patient who has experienced a Grade 4 event; interim analysis results; noncompliance with the protocol; changes in the development plans for the study drug; slow recruitment; and poor-quality data.

10. INVESTIGATIONAL PRODUCTS

Ad-RTS-hIL-12 and Veledimex is an investigational product has two components: the [REDACTED] (Ad-RTS-hIL-12) and veledimex (RTS activator ligand). [REDACTED]

[REDACTED] Veledimex is a small molecule RTS specific transcription factor that stabilizes the RTS promoter components and allows transcription of the hIL-12 target gene. Since target gene expression is dependent on the dose and frequency of veledimex administration, the expression of hIL-12 can be modulated (turned on and off) by the optimal veledimex dose and schedule.

Cemiplimab-rwlc is a covalent heterotetramer consisting of two disulfide-linked human heavy chains, each of which is covalently bonded through disulfide linkages to a human kappa light chain. The antibody possesses an approximate molecular weight of 143.6 kilounified atomic mass unit (kDa) based on the primary sequence. There is a single N-linked glycosylation site on each heavy chain, located within the constant region in the Fc portion of the molecule. The cemiplimab-rwlc heavy chain possesses an IgG4 isotype constant region. The variable domains of the heavy and light chains combine to form PD-1 binding site within the antibody. Please refer to the Pharmacy Manual for additional information.

[REDACTED]

[REDACTED]

[REDACTED]

[REDACTED]

[REDACTED]

is provided in the Pharmacy Manual.

10.2. Preparation of Veledimex

Sponsor will provide veledimex capsules to be dispensed by the study site pharmacy to subjects for oral administration. Information regarding the veledimex is provided in the Pharmacy Manual.

10.3. Preparation of Cemiplimab-rwlc

Cemiplimab-rwlc will be supplied in single-dose vials. Information regarding the preparation of the cemiplimab-rwlc dose is provided in the Pharmacy Manual.

10.4. Handling and Storage

Study drugs must be stored in a restricted access area under the storage conditions indicated in the Investigator's Brochure or Pharmacy Manual. All necessary precautions while handling potentially toxic compounds must be strictly followed.

10.5. Monitoring of Subject Adherence and Managing Missed Doses

10.5.1. Veledimex

The first veledimex dose following Ad-RTS-hIL-12 injection is expected to be administered when the subject is at the clinical site, under careful medical supervision by the clinic staff to ensure that the subject does not have difficulty swallowing the capsules. Thereafter, subjects may be allowed to self-administer the remaining once daily doses as described. Subjects are to be instructed to take the appropriate number of capsules in the same way for each of the remaining treatment period days and may be reminded to do so by phone on non-visit days.

Subjects should NOT make up any missed doses.

Subjects should be instructed to document veledimex dosing compliance in a subject diary, including the time subject took the once daily dose, the time subject ate breakfast, the number of capsules taken, whether subject missed any veledimex doses, and the study day and reason for any missed doses. Study drug container(s) with any remaining capsules should be returned to the study staff on Day 15, so that staff can properly assess dose compliance.

10.5.2. Cemiplimab-rwlc

The recommended dose of cemiplimab-rwlc is 350 mg administered as an intravenous infusion over 30 minutes every 3 weeks (Q3W) until confirmed disease progression or unacceptable toxicity.

10.6. Disposition of Unused Drug

All unused study drug should be destroyed at the study site in accordance with standard institutional practice and in accordance with United States Occupational Safety and Health Administration procedures, after full accountability has been documented. Any study drug destruction at study site must be documented and the records maintained in the investigator's study file.

10.7. Accountability and Dispensation

The investigator must maintain accurate records accounting for the receipt and dispensation of study drugs. The investigational materials are to be prescribed only by the investigator or the sub-investigators named on FDA Form 1572 and may only be dispensed by authorized personnel at the institution(s) listed therein. Under no circumstances will the PI allow the investigational drug(s) to be used for purposes or in subjects other than as directed by the protocol.

10.8. Treatment Plan

10.8.1. Cemiplimab-rwlc

On Day -7, Day 15, and approximately every 3 weeks thereafter subjects will receive cemiplimab-rwlc until confirmed disease progression or unacceptable toxicity.

10.8.2. Ad-RTS-hIL-12 + Veledimex

- Subjects will be given 20 mg of veledimex by mouth, when NPO (excluding other medications) 3 (\pm 2) hours before craniotomy (Day 0). The actual time of veledimex administration should be noted and recorded.
- Surgical planning will be performed on a diagnostic MRI acquired prior to the surgery as per standard of care.
- At the time of tumor resection, tumor, CSF (if available), and blood samples will be collected.
- Immediately after tumor resection, when available, an intraoperative MRI can be performed to identify contrast enhancing or T2/FLAIR hyper intense residual tumor. If intraoperative MRI is not available, the neurosurgeon will select sites for injection.
- [REDACTED]
- [REDACTED]
- The day of Ad-RTS-hIL-12 administration is designated as Day 0. If Ad-RTS-hIL-12 injection is not performed, subject will not continue with post-resection veledimex dosing.
- After tumor resection and Ad-RTS-hIL-12 injection, veledimex will be administered orally for 14 days. The first post-resection veledimex dose is to be given on Day 1. Subsequent veledimex doses are to be taken once daily, in the morning and within approximately 30 minutes of a regular meal.

Subjects should be carefully monitored for possible local reactions and/or hypersensitivity reactions, according to standard practice. Intracranial bleeding or other procedure-related events should be evaluated before the first veledimex dose is given post Ad-RTS-hIL-12 administration. Any changes in neurological status should be reported to the investigator immediately, either during hospitalization or once subject is discharged. Subjects should be instructed to call the study physician or study nurse if they develop any symptoms after they are released from the hospital.

NOTE: It is important that subjects are instructed to maintain adequate oral hydration while subjects are being administered veledimex. Study sites should monitor subjects for proper hydration and monitor blood pressure regularly. The incidence of low blood pressure to date has been lower in glioblastoma subjects as compared with breast cancer or melanoma subjects, likely because a lower dose of veledimex is used in glioblastoma.

10.9. Stopping Rules

From Day -7 to 30 days after completion of Ad-RTS-hIL12 + veledimex dosing, if any subject experienced a death (other than death related to progressive disease); or if any subject, during the initial treatment period (Day -7 to Day 28) experiences a related SAE that has immediately life-threatening consequences requiring urgent intervention or results in death; requires major operative intervention; or is a related grade 4 hematologic toxicity that persists for 5 days: then enrollment of new subjects will be paused, pending review of the event by the Safety Review Committee. The SRC will recommend if changes to the enrollment of additional subjects are

required, including, but not limited to, potentially modifying the dose and schedule of veledimex, to amend the protocol prior to enrollment of additional subjects, or to discontinue enrollment in the study.

10.10. Dose Modifications and Dose Delays

Veledimex dose delays and dose reductions for individual subjects will be allowed in the event of an adverse event, according to the criteria shown in Table 2.

Table 2: Criteria for Dose Delay and Dose Reduction of veledimex

Adverse Reaction	Severity ²	Veledimex Dosage Modifications ¹
Immediately life-threatening/ Potentially-Fatal Severe Adverse Reactions		
Any non-hematologic AE ³	Grade 4 non-hematologic adverse event at least possibly related to study drug, that is considered by the treating physician to be immediately life-threatening, and results in emergent medical and/or surgical intervention	Discontinue
Other Severe Adverse Reactions		
Cytokine Release Syndrome	Grade 3 or higher (per the Ziopharm Working Definition of Cytokine Release Syndrome)	Withhold ⁴
Any non-hematologic AE ^{3, 5} (except brain edema)	Grade 3 or higher non-hematologic adverse event that is at least possibly related to study drug and persists at least 3 days	Withhold ⁴
Cerebral edema ⁵	Grade 3 or higher	Withhold ^{4, 6}
Thrombocytopenia	Grade 3 or higher thrombocytopenia (< 50,000/mm ³) at least possibly related to study drug	Withhold ⁴
Lymphopenia or other hematologic toxicity	Grade 4 or higher lymphopenia or other hematologic toxicity (except thrombocytopenia)	Withhold ⁴
Increased transaminitis ⁸	Grade 3 or higher increase in ALT or AST	Potentially Withhold ⁷

1. These recommendations are for general guidance only. Treating physicians should manage patients according to their clinical judgement, as informed by institutional guidelines, best practices and these guideline recommendations.
2. Toxicity as graded per National Cancer Institute Common Terminology Criteria for Adverse Events, Version 5.0.
3. Nausea and vomiting will not be considered in this category unless at least Grade 3 or 4 and refractory to antiemetics (i.e., defined as symptoms not mitigated by maximal medical support as directed by the Investigator (per institutional guidelines) in consultation with the Sponsor Clinical Medical Monitor).
4. Withhold the next and any successive doses of veledimex while the Grade 3 or 4 toxicity persists. Veledimex dosing may resume, after discussion with the Sponsor Clinical Medical Monitor, in subjects with rapid and substantial reversal of toxicity, either spontaneously or following appropriate medical treatment. The Sponsor Clinical Study Coordinator will be notified in advance of veledimex dosage modifications.
5. Seizures, headache, and cerebral edema are commonly observed in this population and will be recorded according to the grade of toxicity and therefore will not be considered in this category unless unresponsive to maximal medical support as directed by the Investigator (informed by institutional guidelines) and in consultation with the Sponsor Clinical Medical Monitor.
6. *Cerebral Edema Guideline Recommendations:* As a general guideline, mannitol (Osmotrol), corticosteroid treatment (i.e., dexamethasone or Decadron) and/or withholding the next dose(s) of veledimex short-term are considered for cerebral edema, CTCAE v5.0 Grade 3 (or for “moderate” severity descriptively). For Grade 4 cerebral edema, mannitol (Osmotrol), higher dose corticosteroids and/or longer-term withholding or discontinuation of veledimex are considered, especially if the edema is not sufficiently mitigated by urgent medical intervention. It is expected that the use of corticosteroids will vary between sites and among subjects, and therefore, the precise extent and dosage of steroids cannot be specified per protocol. The treating physician will decide as is safe and appropriate for the individual subject according to their clinical judgement as informed by the label and institutional guidelines and should consider the minimum steroid dose or the lowest amount that adequately and

rapidly controls the subject's signs and symptoms (refer to Rationale section below). Consideration also may be given to a limited number of doses of bevacizumab (Avastin) if (typically high-dose) corticosteroids are not in the best interests of the subject in the treating physician's clinical judgement and following consultation with the Medical Monitor. In the event of an immediately life-threatening event, the treating physician should consider surgical decompression.

7. *Rationale:* Cerebral edema may pre-exist experimental treatment to a variable extent and usually is associated with the underlying disease and/or increase following surgical procedures. The study treatment, particularly with combination therapy including an immune checkpoint inhibitor, also may possibly cause an increase in the severity of edema. Patients with glioblastoma receiving more than 4 mg dexamethasone qd were reported to have decreased overall survival, possibly due to immunosuppression (British J Cancer 2015;113, 232-241). Preliminary data presented at the Society for Neuro-Oncology 2018 Annual Meeting by Ziopharm Oncology also suggests that overall survival is decreased in 20 mg veledimex craniotomy cohort subjects (i.e., administered more than a 20 mg cumulative dosage of dexamethasone) during the initial treatment period (Days 0-14); the relative contributions of severity of the condition vs immunosuppression to the negative effect observed on overall survival are presently uncertain.
8. Withhold the next dose(s) of veledimex if the transaminitis is part of a constellation of findings consistent with Cytokine Release Syndrome (refer to Ziopharm Working Definition of Cytokine Release Syndrome). The treating physician may elect to follow the laboratory test trajectory and clinical status if an isolated transaminitis.

Cemiplimab-rwlc dose delays and dose reductions for individual subjects will be allowed in the event of an adverse event, according to the criteria shown in Table 3.

Table 3: Criteria for Dose Delay and Dose Reduction of cemiplimab-rwlc

Adverse Reaction	Severity	Cemiplimab-rwlc Dosage Modifications
Severe and Fatal Immune-Mediated Adverse Reactions		
Pneumonitis	Grade 2	Withhold*
	Grades 3 or 4	Permanently discontinue
Colitis	Grades 2 or 3	Withhold*
	Grade 4	Permanently discontinue
Hepatitis	If AST or ALT increases to more than 3 and up to 10 times the upper limit of normal (ULN) or if total bilirubin increases up to 3 times the ULN	Withhold*
	If AST or ALT increases to more than 10 times the ULN or total bilirubin increases to more than 3 times the ULN	Permanently discontinue
Endocrinopathies	Grades 2, 3, 4	Withhold if clinically necessary*
Other immune-mediated adverse reactions involving a major organ	Grade 3	Withhold*
	Grade 4	Permanently discontinue
Recurrent or persistent immune-mediated adverse events	
 • Recurrent Grades 3 or 4 • Grades 2 or 3 persistent for 12 weeks or longer after last cemiplimab-rwlc dose in spite of appropriate therapy • Requirement for 10 mg per day or greater prednisone or equivalent lasting 12 weeks or longer after last cemiplimab-rwlc dose 	Permanently discontinue
Severe and Fatal Immune-Mediated Adverse Reactions		
Infusion-related reactions	Grades 1 or 2	Interrupt or slow the rate of infusion
	Grades 3 or 4	Permanently discontinue

AE = adverse event

*: Resume in patients with complete or partial resolution (Grade 0 to 1) after supraphysiologic dose of corticosteroids discontinued

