Neurological	Grade 2 decreased level of consciousness (e.g., slow response to stimuli; limiting instrumental activities of daily living)													
GI	Grade 2 or 3 headache Grade 2 nausea or vomiting													
Grade 3	Symptoms that require and respond to aggressive interventions and occurrence of any of the following:													
	
 1. Hypotension requiring high dose or multiple vasopressors 2. Oxygen requirement \geq 40% 3. Grade 4 transaminitis (ALT/AST), lymphopenia, or Grade 3 organ toxicities, e.g.: 
 
 Hematologic	\geqGrade 3 febrile neutropenia, or platelets decrease/thrombocytopenia	
 
 Renal	Grade 3 creatinine increase	
 
 Cardiac	Grade 3 arrhythmia, or acute heart failure	
 
 Pulmonary	Grade 3 pulmonary edema, or dyspnea	
 
 4. Other symptoms, e.g.: 
 
 Neurological	Grade 3 decreased level of consciousness (e.g. difficult to arouse)	
 
 GI	Aseptic meningitis Grade 3 nausea or vomiting	
 
 		Hematologic	\geq Grade 3 febrile neutropenia, or platelets decrease/thrombocytopenia	Renal	Grade 3 creatinine increase	Cardiac	Grade 3 arrhythmia, or acute heart failure	Pulmonary	Grade 3 pulmonary edema, or dyspnea	Neurological	Grade 3 decreased level of consciousness (e.g. difficult to arouse)	GI	Aseptic meningitis Grade 3 nausea or vomiting
Hematologic	\geq Grade 3 febrile neutropenia, or platelets decrease/thrombocytopenia													
Renal	Grade 3 creatinine increase													
Cardiac	Grade 3 arrhythmia, or acute heart failure													
Pulmonary	Grade 3 pulmonary edema, or dyspnea													
Neurological	Grade 3 decreased level of consciousness (e.g. difficult to arouse)													
GI	Aseptic meningitis Grade 3 nausea or vomiting													
Grade 4	Life-threatening symptoms and occurrence of any of the following:													

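### For a Grade 4 cytokine release syndrome event that meets both rows, Table 2 tells sites to discontinue veledimex in one row and to withhold it in another, with no stated order between them

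*Protocol*

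**What the plan says.** Section 10.10, Table 2 is laid out in two blocks. The first block is for immediately life-threatening or potentially fatal reactions and has a single row, covering any non-hematologic adverse event. That row is triggered by a "Grade 4 non-hematologic adverse event at least possibly related to study drug, that is considered by the treating physician to be immediately life-threatening"; a further condition is that emergency treatment, whether medical or surgical, follows. The action is Discontinue.

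The second block is headed as other severe reactions. Its CRS row is triggered at "Grade 3 or higher (per the Ziopharm Working Definition of Cytokine Release Syndrome", and the action is Withhold, with note 4 attached. Note 4 says "Withhold the next and any successive doses of veledimex while the Grade 3 or 4 toxicity persists", and then: "Veledimex dosing may resume, after discussion with the Sponsor Clinical Medical Monitor, in subjects with rapid and substantial reversal of toxicity".

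Appendix 1 is the sponsor's CRS grading scale, which section 10.11 makes the scale for this event. It introduces Grade 4 as "Life-threatening symptoms and occurrence of any of the following" and lists a need for ventilator support, or Grade 4 organ toxicities such as respiratory failure, cardiac arrest, coma or renal failure needing dialysis. Grade 5 is death.

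Note 1 to Table 2 describes its recommendations as general guidance, to be applied with clinical judgement.

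**The concern.** CRS has its own row in Table 2 and its own grading scale. For its most severe survivable grade, a site can find two instructions in one table: a stop without return, and a hold from which dosing may resume. Section 10 of the protocol describes veledimex as the switch for IL-12 expression, so the difference is whether that expression may be turned on again after a life-threatening reaction.

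The ambiguity also reaches the reporting. SAP section 9.1.7 tabulates events whose action taken was drug withdrawn, and the SAP's table list has separate tables for events leading to discontinuation and to interruption of study medication. The same event could fall in either, depending on which row the site followed. Section 9.4 of the protocol requires withdrawal for treatment-related events that meet withdrawal criteria, so the criterion for this event should be readable in one way.

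**Working it through.** No arithmetic applies, and the plan gives no figure to reproduce. The check is whether one event can satisfy both rows.

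| | First row | CRS row |
|---|---|---|
| Event | Any non-hematologic adverse event | CRS |
| Grade | 4 | 3 or higher |
| Relatedness | At least possible | No condition |
| Physician's judgement | Immediately life-threatening | No condition |
| Intervention | Emergent medical or surgical | No condition |
| Action | Discontinue | Withhold; may resume (note 4) |

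**Does the first row reach CRS?** Appendix 1 describes CRS as a multi-system immune disorder, not a hematologic toxicity, and the first row does not carve it out. Elsewhere in the table exceptions are written where they are wanted: brain edema is excepted from the general Withhold row and thrombocytopenia from the hematologic row. No exception mentions CRS.

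**Does the CRS row reach Grade 4?** Its trigger has no upper limit, and Grade 5 is death. For a surviving subject, higher than Grade 3 can only mean Grade 4. Note 4 also names Grade 4.

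Case by case:

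1. Grade 3 CRS meets the CRS row but not the first row. No conflict.
2. Grade 4 CRS that fails any of the first row's three further conditions (relatedness, physician's judgement, emergent intervention) meets the CRS row only. No conflict.
3. Grade 4 CRS that satisfies all three meets both rows, with different actions. A related event needing ventilator support would ordinarily be of this kind.

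The general non-hematologic row in the second block (Grade 3 or higher, at least possibly related, lasting at least 3 days) may also apply in case 3. It too says Withhold, so it does not settle the question.

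**Is precedence stated?** Not in the table, its notes or Appendix 1. Cerebral edema, in the same block, has note 6, which treats Grade 3 and Grade 4 separately. CRS has no such note.

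**The case against.** The strongest answer is the layout. If the second block is for *other* severe reactions, an event that qualifies for the first block is not an *other* reaction, and the first row governs. The general non-hematologic rows follow the same pattern: Discontinue in the first block, Withhold in the second. Unless the blocks are tiers, the table would conflict for those events too. This is a reasonable reading and probably the one a careful reader would reach. It remains an inference: no sentence states it, and a site looking up CRS finds a dedicated row that reaches Grade 4 and says Withhold.

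One might also say that the rows use different scales, since note 2 grades toxicity by CTCAE and CRS has its own scale. The first row does not say that this removes CRS from its scope. The organ toxicities that define Grade 4 CRS can themselves be Grade 4 non-hematologic events, while section 14.2 tells sites to record the diagnosis, not its symptoms.

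The safeguards are real and stand. Table 2 is guidance. Resumption is permissive, needs rapid and substantial reversal, and follows discussion with the Medical Monitor. Veledimex after the injection lasts 14 days and missed doses are not made up (sections 10.8.2 and 10.5.1), so any window for resuming is short. Section 10.9 pauses enrollment for committee review after a related, immediately life-threatening serious event in the initial treatment period, though that protects new subjects and does not tell the site what to do for the affected one. Note 4 is shared by five Withhold rows, one of them for Grade 4 hematologic toxicity, so its mention of Grade 4 is weak evidence that resumption after life-threatening CRS was intended.

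Four stronger readings should be resisted:

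- **That every Grade 4 CRS event is caught.** The first row's three conditions exclude some.
- **That section 9.6 contradicts note 4.** It lists a "decision to re-challenge patient who has experienced a Grade 4 event" among events that may trigger closing the study or a center. That presupposes re-challenge can happen and attaches a possible consequence; it does not forbid it.
- **That section 14.4 settles the matter.** Its general Grade 4 wording refers to stopping the drug, but applies to events CTCAE does not define, whereas section 10.11 gives CRS its own scale.
- **That a number of affected subjects can be given.** The documents contain no Grade 4 CRS rate, and an all-grade rate would not serve, since Appendix 1 counts flu-like symptoms as Grade 1.

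**Conclusion.** The point holds within limits. It covers Grade 4 CRS that is at least possibly related, judged immediately life-threatening and treated emergently; for those events Table 2 gives two different actions and no order between them. The headings favor the first row but do not settle it.

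The conclusion rests on the wording of Table 2 and Appendix 1 in the current protocol, and on reading CRS as non-hematologic. Its practical size is limited by the guidance status of the table and the Medical Monitor's involvement. It bears on the handling of individual subjects and on how such an event is tabulated, not on the sample size or the survival analysis. No view is taken on which action is clinically right.

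**What to change.** Reconcile the CRS row, note 4 and the first row so that a single instruction applies to Grade 4 CRS. A sentence stating which row takes precedence when an event meets more than one would do it; separating Grade 3 from Grade 4 in the CRS row, as Table 3 does for several cemiplimab reactions, is another route. The sponsor's clinical team decides which instruction applies. Section 9.6 needs no change.

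The cost is protocol wording or a clarification memo to sites. The SAP already describes 40 treated subjects. If veledimex dosing is complete, the study report should say how any such event was handled and classified, and the wording should be corrected before Table 2 is reused in another protocol.
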